### 7.2 PARTICIPANT DISCONTINUATION/WITHDRAWAL FROM THE STUDY

Based on the NIH Behavioral and Social Intervention Clinical Trial Protocol Template v3.0 - 20180827

Participants are free to withdraw from participation in the study at any time upon request. An investigator may discontinue a participant from the study for the following reasons:

- Participant becomes dangerous to self or others.
- Lost-to-follow up; unable to contact subject (see Section 7.3, Lost to Follow-Up)
- Any event or medical condition or situation occurs such that continued collection of follow-up study data would not be in the best interest of the participant or might require an additional treatment that would confound the interpretation of the study
- The participant meets an exclusion criterion (either newly developed or not previously recognized) that precludes further study participation

The reason for participant discontinuation or withdrawal from the study will be recorded on the attrition Case Report Form (CRF). Subjects who sign the informed consent form and are randomized but do not receive the study intervention may be replaced. Subjects who sign the informed consent form, and are randomized and receive the study intervention, and subsequently withdraw, or are discontinued from the study, will not be replaced. If the subject becomes ineligible, then we will replace the subject but only if the study is within the specified recruitment period.

We will attempt to obtain a final questionnaire assessment and saliva sample (if necessary per protocol) from all subjects who withdraw from the study for any reason. We will make a minimum of 5 attempts to contact the subject in cases of withdrawal and those who relocate.

This study may be suspended or prematurely terminated if there is sufficient reasonable cause. Written notification, documenting the reason for study suspension or termination, will be provided by the suspending or terminating party to investigator and NIDCR. If the study is prematurely terminated or suspended, the principal investigator will promptly inform the IRB and will provide the reason(s) for the termination or suspension. Circumstances that may warrant termination include, but are not limited to:

- Determination of unexpected, significant, or unacceptable risk to subjects.
- Insufficient adherence to protocol requirements.
- Data that are not sufficiently complete and/or evaluable.
- Determination of futility.

### 7.3 LOST TO FOLLOW-UP

At each assessment point, we will continue to contact participants even if they have not answered one or all of the prior assessments. At each assessment point, we will attempt to contact participants a minimum of 5 times through phone, text, email, and letters. We will use paid services and the EDR to get up to date phone numbers for those that are no longer in service.

The following actions must be taken if a study subject fails to complete a required follow-up assessment:

- The study team will attempt to contact the participant, and counsel the participant on the importance of maintaining the assigned assessment schedule.
- Before a participant is deemed lost to follow-up, the investigator or designee will make every effort to regain contact with the participant as stated above. These contact attempts will be documented in the participant's study file. Participants who are lost to follow-up will be attempted again at the next follow-up.

## 8 STUDY ASSESSMENTS AND PROCEDURES

### 8.1 ENDPOINT AND OTHER NON-SAFETY ASSESSMENTS

Participants must be screened for eligibility criteria before they are enrolled in the study. The timeline is as follows:

#### **Time 0:** Pre-enrollment

- Boston University GSDM patients and TU School of Dental Medicine patients will be identified and screened within approximately 4-weeks of their scheduled dental appointment at the respective dental clinics. The majority of the screening questions can be answered with 'Yes', 'No', or 'Prefer not to answer'. Participants who select 'Prefer not to answer' will be ineligible for study participation. Screening will be discontinued if participants answer, 'No' or 'Prefer not to answer' to 'Have you smoked any cigarettes (do not include e-cigarettes or vaping in your answer) in the past 7-days?'.
- If participants meet all eligibility criteria, they will continue to mobile number verification. If the number is verified, the participant meets all criteria for study participation and can continue to informed consent.
- Informed consent will be obtained either verbally or electronically. Contact information will be collected after informed consent.

#### **Time 1:** Dental clinic appointment

- At the dental clinic appointment, all participants will be rescreened to confirm smoking status. Those who self-report no smoking in the past 7 days will be terminated.
- Consented participants who do not complete the baseline questionnaire before the start of their dental appointment will also be terminated if a new dental appointment is not scheduled within 45 days of the date they completed screening.

Endpoints and outcome measures:

- Evidence-based treatments (EBTs) for smoking cessation (assessed at Time 4 – 6). The EBTs for smoking cessation that will be assessed are: 1) the state quitline (operated by National Jewish Health; objective utilization of phone counseling services which also include the number of counseling calls completed, and eligibility for, and provision of, nicotine replacement therapy); 2) the NCI SmokefreeTXT (objective utilization of SmokefreeTXT, the NCI text-message program for smoking cessation, which also includes length of program utilization, and program engagement); 3) clinic-based cessation services (self-report utilization of smoking cessation

counseling, either individual or group sessions, offered by community health centers, hospitals or clinics, which also includes the number of sessions attended, and the provision and use of pharmacologic treatments); 4) pharmacologic treatment (utilization of nicotine replacement therapy products such as the nicotine patch, gum or lozenge, and the nicotine spray or inhaler, and non-nicotine medications such as Zyban, Wellbutrin or Bupropion, Chantix or Varenicline, obtained through physician prescription or, in the case of nicotine replacement products, through the quitline or purchased by participants). Depending on the method of pharmacologic treatment acquisition, pharmacologic treatment utilization may be objective or self-report. Acquisition of nicotine replacement therapy will be verified if participants receive them from the state quitline.

- EBTs for smoking cessation will be operationalized as: 1) utilization of any EBT over the 7-month study period; 2) total number of EBTs utilization during the 7-month study period (ranging 0 to 4); 3) EBT utilization index score (UIS; obtained by first computing a proportion of utilization score for each of the EBTs for each participant, and then adding up the individual proportion scores; see section 9.4.1 for details); 4) combination of at least one form of non-pharmacologic EBT and at least one form of pharmacologic EBT over the 7-month study period.
- Quit smoking attempts (assessed at Time 4 – 6). The number of quitting smoking attempts participants have made, since last contact, that have lasted 24 hours or more and that were not due to hospitalization or illness.
- Motivation to quit smoking (assessed at Time 4 – 6). Participants' motivation to quit smoking within 30 days (yes vs no).
- Smoking abstinence (assessed at Time 4 – 6). Seven-day point-prevalence abstinence (7-day ppa) assessed by self-report of no smoking, not even a puff, in the past 7 days and salivary cotinine level < 15 ng/mL.
- Mediators of treatment effects (assessed at Time 2 – 6). Theoretically driven constructs hypothesized to mediate any observed intervention effect (EBT utilization, quit smoking attempts, motivation to quit, or smoking abstinence) include the social cognitive theory constructs of motivation, self-efficacy, and outcome expectancies.
- Moderators or treatment effects (assessed at baseline). Moderating factors include sex, race or ethnicity, perceived stress and readiness to quit smoking.

## 8.2 SAFETY ASSESSMENTS

N/A

## 8.3 ADVERSE EVENTS AND SERIOUS ADVERSE EVENTS

### 8.3.1 DEFINITION OF ADVERSE EVENTS

This protocol uses the definition of adverse event from 21 CFR 312.32 (a): any untoward medical occurrence associated with the use of an intervention in humans, ***whether or not considered intervention-related***.

### 8.3.2 DEFINITION OF SERIOUS ADVERSE EVENTS

Based on the NIH Behavioral and Social Intervention Clinical Trial Protocol Template v3.0 - 20180827

A serious adverse event (SAE) is one that meets one or more of the following criteria:

- Results in death
- Is life-threatening (places the subject at immediate risk of death from the event as it occurred)
- Results in inpatient hospitalization or prolongation of existing hospitalization
- Results in a persistent or significant disability or incapacity
- Results in a congenital anomaly or birth defect
- An important medical event that may not result in death, be life threatening, or require hospitalization may be considered an SAE when, based upon appropriate medical judgment, the event may jeopardize the subject and may require medical or surgical intervention to prevent one of the outcomes listed in this definition.

---

### 8.3.3 CLASSIFICATION OF AN ADVERSE EVENT

---

#### 8.3.3.1 SEVERITY OF EVENT

The following scale will be used to grade adverse events:

1. Mild: no intervention required; no impact on activities of daily living (ADL)
2. Moderate: minimal, local, or non-invasive intervention indicated; moderate impact on ADL
3. Severe: significant symptoms requiring invasive intervention; subject seeks medical attention, needs major assistance with ADL

---

#### 8.3.3.2 RELATIONSHIP TO STUDY INTERVENTION/EXPERIMENTAL MANIPULATION

To assess relationship of an event to study intervention, the following guidelines will be used:

1. Related (Possible, Probable, Definite)
  - a. The event is known to occur with the study intervention.
  - b. There is a temporal relationship between the intervention and event onset.
  - c. The event abates when the intervention is discontinued.
  - d. The event reappears upon a re-challenge with the intervention.
2. Not Related (Unlikely, Not Related)
  - a. There is no temporal relationship between the intervention and event onset.
  - b. An alternate etiology has been established.

---

#### 8.3.3.3 EXPECTEDNESS

The study PI will be responsible for determining whether an AE is expected or unexpected. An adverse event will be considered unexpected if the nature, severity, or frequency of the event is not consistent with the risk information previously described for the intervention.

---

### 8.3.4 TIME PERIOD AND FREQUENCY FOR EVENT ASSESSMENT AND FOLLOW-UP

AEs, UPs and SAEs will be recorded in the data collection system throughout the study. Events will be followed for outcome information until resolution or stabilization.

---

### 8.3.5 ADVERSE EVENT REPORTING

Based on the NIH Behavioral and Social Intervention Clinical Trial Protocol Template v3.0 - 20180827

Adverse events that are related to the study (possibly, probably, or definitely related) will be recorded and reported throughout the entire study. The principal investigator will report, in summary form, all AEs to the IRB at the time of continuing review.

---

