At the teeth cleaning appointment, all participants will receive a Viotek Spectre virtual reality and earbuds with volume control. A study smartphone (iPhone) will be inserted into the headset and programmed to show either the intervention or the control video, depending upon the patient's randomization. Both videos will be the same duration (10 minutes). Participants randomized to the Intervention group will watch one of two videos dependent upon their latest assessment of motivation to quit (assessed at the dental clinic appointment). If the participant is motivated to quit within 30 days, they will watch the "Ready to Quit" video; those not motivated to quit within 30 days will watch the "Not Ready to Quit" video. The RA will help the participant adjust the headset for comfort and use the audio control on the earbuds to ensure the volume is set at a level where the participant is able to hear the practitioner while watching the video. Participants will be advised to raise their hand to signal for adjustments, removal of the headset, or the conclusion of the video.

Shortly after participants complete watching the assigned video, the RA will trigger the post-video questionnaire in REDCap. The post-video questionnaire will be delivered as e-link through text message and email to all participants. Participants will be required to complete this questionnaire in their own time within 10 days of receiving the e-link invitation.

Within 24 hours of randomization, the Intervention group will begin the 4-week text message curriculum program that has been designed in preparatory research to: a) motivate EBT contact and utilization, b) facilitate transition to EBTs, c) dispel myths and misinformation about EBTs, and d) measure mediators weekly. There are two different tracks of text messages to motivate EBT contact and utilization: one for those who are motivated to quit and one those who are not motivated to quit. The Control group will receive assessment-only text messages, and will follow the same schedule as the assessment text messages in the intervention group (e.g., one text message to assess motivation, one to assess self-efficacy, and one to assess outcome expectancies each week for three weeks). All participants will be able to connect to, and access the services of, one or more EBT resources at any point during the study: both groups receive this information at the dental clinic visit via brochure, and the Intervention group

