### 8.3.6 SERIOUS ADVERSE EVENT REPORTING

For any AE meeting the specified Serious Adverse Event criteria, the PI or designee will submit an SAE form to NIDCR's centralized safety system via Rho Product Safety. This report may be sent by fax or email. Once submitted, Rho Product Safety will send a confirmation email to the investigator within 1 business day. The investigator should contact Rho Product Safety if this confirmation is not received. This process applies to both initial and follow-up SAE reports.

SAE Reporting Contact Information:

- Product Safety Fax Line (US): [name]
- Product Safety Fax Line (International): [contact]
- Product Safety Email: rho\[contact]

General questions about SAE reporting can be directed to the Rho Product Safety Help Line (available 8:00AM – 5:00PM Eastern Time):

- US: [name]
- International: [contact]

The study clinician will complete a Serious Adverse Event Form and submit via fax or email within the following timelines:

- All deaths and immediately life-threatening events, whether related or unrelated, will be recorded on the Serious Adverse Event Form and submitted to Product Safety within 24 hours of site awareness.
- Serious adverse events other than death and immediately life-threatening events, regardless of relationship, will be reported by fax within 72 hours of site awareness.

All SAEs will be followed until resolution or stabilization.

The principal investigator will report, in summary form, all SAEs to the IRB at the time of continuing review.

---

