#### 9.4.4 SAFETY ANALYSES

N/A

---

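### Section 8.3.5 names only related adverse events for recording, in conflict with 8.3.1 and 8.3.4, and 9.4.4 plans no adverse event summary by arm

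*Combined protocol and SAP*

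**What the plan says.** Section 8.3.1 of the combined protocol and SAP takes an adverse event to be "any untoward medical occurrence associated with the use of an intervention in humans", and adds "whether or not considered intervention-related". Section 8.3.4 says "AEs, UPs and SAEs will be recorded in the data collection system throughout the study". Section 10.1.9.1 has adverse event data entered in REDCap. Neither of those two sections makes entry depend on causality. Section 8.3.3.2 provides a class for events that are not related.

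Section 8.3.5 then says "Adverse events that are related to the study (possibly, probably, or definitely related) will be recorded and reported throughout the entire study". Its next sentence says "The principal investigator will report, in summary form, all AEs to the IRB at the time of continuing review".

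Serious events have their own rule in 8.3.6: "All deaths and immediately life-threatening events, whether related or unrelated, will be recorded on the Serious Adverse Event Form". The same section has other serious events reported whatever their relationship.

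The schedule in 1.3 marks adverse event reporting at every time point from the clinic visit (Time 1) to Time 6. Section 8.2 (safety assessments) and section 9.4.4 (safety analyses) both read N/A.

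**The concern.** If 8.3.5 is the working rule, causality is judged before anything is written down. A non-serious event judged unrelated then leaves no record, and nobody can later ask whether that judgement was sound. This matters because other parts of the plan depend on counts. Sections 8.3.3.3 and 8.4.1 both include how often an event occurs among the criteria for calling it unexpected. An event dismissed as unrelated one case at a time cannot be recognised as unusually frequent if the cases were never logged.

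The plan does not say who judges relatedness. The principal investigator judges expectedness (8.3.3.3), has primary responsibility for safety oversight (10.1.6) and is unmasked (6.3). A complete record would be the natural check on judgements made under those conditions.

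The N/A in 9.4.4 is a separate gap. The trial schedules adverse event collection over the whole follow-up but does not say how the data will be summarised for either arm.

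**Working it through.** No arithmetic applies; the check compares the rules by class of event.

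| Event class | AE under 8.3.1? | 8.3.4 and 10.1.9.1 | 8.3.5, first sentence | 8.3.5, IRB summary | 8.3.6 |
|---|---|---|---|---|---|
| Serious, related | Yes | Recorded | Recorded and reported | Included | Captured |
| Serious, not related | Yes | Recorded | Not named | Included | Captured |
| Non-serious, related | Yes | Recorded | Recorded and reported | Included | Does not apply |
| Non-serious, not related | Yes | Recorded | Not named | Included | Does not apply |

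For serious unrelated events, 8.3.6 fills the gap left by 8.3.5. Only the last row is unresolved: two sections say record, one sentence implies otherwise, and the next sentence assumes the record exists.

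There are three ways to read the last row:

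1. The first sentence of 8.3.5 governs recording. Unrelated non-serious events are then not logged. This contradicts 8.3.4, and the IRB cannot receive a summary of all events.
2. Section 8.3.4 governs recording, and 8.3.5 limits only reporting to related events. The record is then complete, but the limit on reporting contradicts the IRB sentence that follows it, and the word recorded in the first sentence has no function.
3. Everything is recorded and everything is summarised to the IRB. This fits 8.3.1, 8.3.4 and the IRB sentence, but the first sentence of 8.3.5 then restricts nothing.

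No reading gives every sentence an effect without a contradiction. Staff at the two clinics could reasonably adopt different readings.

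Headset discomfort is a listed risk (2.3.1), and its recording is also left open. Under 2.3.3, a participant who takes the headset off because it is uncomfortable has participation ended. Under 7.1, one who cannot or will not wear it is classed as having become ineligible once randomised, and 7.2 allows replacement. None of these sections says whether an adverse event is logged. Such a participant could appear in the data only as an eligibility failure.

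For the analysis, 1.3 collects adverse events at Times 1 to 6, 9.4.4 specifies nothing, and no other part of section 9 mentions adverse events. No summary by arm is therefore planned, even for serious events, which are captured in full.

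**The case against.** The best defence is that 8.3.4 deals with recording and 8.3.5 with reporting, so the record is complete and 8.3.5 is only loosely worded. The unfiltered REDCap entry in 10.1.9.1 and the not-related class in 8.3.3.2 support this, and the manual of procedures (6.2.1) may settle the matter. It is a plausible account of the intent. It does not rescue the text, because 8.3.5 itself says which events are recorded.

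It is also fair to say that the named risks (headset discomfort, accidents while texting, thumb and joint pain) are the events most readily judged at least possibly related. Section 8.3.5 would keep most of them; what it may lose is mainly unrelated illness. This stands, and it limits the consequence. A by-arm table would not isolate harm from the headset either, since both arms wear the same one for the same time. It would still describe the events, and it would contrast the arms on the text programme, which does differ.

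A reader might go further in three ways that the documents do not support:

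- **That only related events are recorded.** Section 8.3.6 captures serious events regardless of relationship, and 8.3.4 has no filter.
- **That the trial cannot support its minimal-risk statement.** The wording in 2.3.1 and 2.3.3 is a classification made in advance. No objective, endpoint or hypothesis tests it.
- **That capture differs by arm because the Intervention arm receives more texts.** This would require adverse events to be reported spontaneously. The questionnaire contents in 1.3 are given only as examples, so an adverse event question may exist. Adverse event reporting has its own schedule row, not split by arm, and 6.4 describes monitoring of participants' incoming texts without distinguishing the arms. More texts also mean more exposure to text-related risk, so contact frequency alone would not show reporting bias.

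**Conclusion.** The point holds in limited form. Section 8.3.5 is wrong as written: its first sentence conflicts with 8.3.1, 8.3.4, 10.1.9.1 and the sentence that follows it. The conflict covers one class, non-serious events judged unrelated. If 8.3.5 is followed literally, that class goes unrecorded, the relatedness judgement cannot be audited, and the promised IRB summary cannot be complete. The text alone establishes the contradiction; the lost records depend on staff following that sentence, which the documents neither confirm nor exclude.

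The missing plan in 9.4.4 is a gap that is cheap to close, not an error that biases a result. No efficacy analysis is affected.

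The size cannot be given as a number. The documents state no expected adverse event rate and no capture rate, and a figure built on assumed capture would describe the assumption rather than the trial.

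**What to change.** 1. Reconcile 8.3.1, 8.3.4 and 8.3.5 so that all adverse events are recorded whether or not related, with relatedness as a recorded attribute. If a narrower set is to be reported, state that set separately and make it agree with the IRB summary sentence. State that headset discomfort leading to removal (2.3.3), or to the post-randomisation ineligible status (7.1), is also logged as an adverse event.
2. Replace N/A in 9.4.4 with a descriptive table by randomised arm: numbers and percentages of participants with any adverse event, any related adverse event and any serious adverse event, broken down by severity and relatedness. No hypothesis test is needed. Section 9.4.1 says a formal SAP will be completed before unblinding, so the table can be specified there too.

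The cost is a wording amendment, more minor unrelated events to log, and one extra table.

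A new symptom question in the follow-up forms is not part of this fix. The current version is dated 12 September 2024, the study period ends on 31 July 2025 (1.1), and each participant is followed for 7 months. Counting back 7 months from the end of July 2025 puts the last randomisation at about the turn of the year. A new question would probably reach only later participants or later visits, which would mix two capture methods over calendar time.
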